5.4.2. PK Parameter Analysis Set

The PK parameter analysis population is defined as all enrolled patients treated who have sufficient information to estimate at least 1 of the PK parameters of interest.

5.4.3. PD/Biomarker analysis set

The PD/Biomarker analysis population is defined as all enrolled patients with at least 1 of the PD/Biomarker evaluated at pre- and/or post-dose, and measurable PK concentrations.

5.5. Treatment Misallocations

This is an unblinded MTD dose finding study. Patients will be included in the cohort based on their actual treated dose.

5.6. Protocol Deviations

Protocol deviations will be defined and this analysis plan to be updated before database lock.

5.6.1. Deviations assessed prior to randomization

At Screening, the investigator will assess subjects against the inclusion and exclusion criteria as set out in Sections 4.1 and 4.2 of the protocol.

5.6.2. Deviations assessed post-randomization

A full list of protocol deviations for the study report will be compiled prior to database closure. Any significant deviation from the protocol will be reviewed prior to database closure and a decision taken regarding evaluation for each analysis population.

5.7. Baseline and Covariates

Baseline measurement is defined as the planned Baseline visit measurement prior to the first dose of study medication administration; otherwise, the last available measurement prior to the first dose of study medication administration is to be adopted as Baseline.

5.8. Efficacy Endpoints

In this First in Patient study anti-tumor activity is a secondary objective.

RECIST 1.1 objective tumor response criteria are stated below:

Evaluation of target lesions:

Complete Response (CR): Disappearance of all target lesions. Any pathological lymph nodes (whether target or non-target) must have reduction in short axis to <10 mm.

Partial Response (PR): At least a 30% decrease in the sum of diameters of target lesions, taking as reference the baseline sum diameters.

Progressive Disease (PD): At least a 20% increase in the sum of diameters of target lesions, taking as reference the smallest sum on study (this includes the baseline sum if that is the smallest on study). In addition to the relative increase of 20%, the sum

must also demonstrate an absolute increase of at least 5 mm. (Note: the appearance of one or more new lesions is also considered progression).

Stable Disease (SD): Neither sufficient shrinkage to qualify for PR nor sufficient increase to qualify for PD, taking as reference the smallest sum diameters while on study.

Evaluation of non-target lesions:

Complete Response (CR): Disappearance of all non-target lesions and normalisation of tumour marker level. All lymph nodes must be non-pathological in size (<10 mm short axis).

Non-CR/Non-PD: Persistence of one or more non-target lesion(s) and/or maintenance of tumour marker level above the normal limits.

Progressive Disease (PD): Unequivocal progression (see comments below) of existing non-target lesions. (Note: the appearance of one or more new lesions is also considered progression).

Following assessments are to be summarized:

- **Overall Response Rate (ORR)** - ORR is defined as the percentage of patients with best overall response (BOR) of CR or PR relative to the appropriate analysis set.

Category of Best Overall Response:

Best overall response: The **BOR** is the best response recorded from start date until the end of study, disease progression or start of new anti-cancer therapy whichever is earlier. Due to the tumor response is not a primary endpoint, CR or PR assessment based on RECIST 1.1 does not require confirmation.

CR: Complete response is defined (per RECIST 1.1) as disappearance of all target and non-target lesions. Any pathological lymph nodes (whether target or non-target) must have reduction in short axis to <10 mm.

PR: Partial response is defined (per RECIST 1.1) as at least a 30% decrease in the sum of diameters of target lesions, taking as reference the baseline sum diameters.

SD: At least one objective status of stable or better documented at least 6 (-5 Days) weeks (in consideration of study monitoring schedule) after start date and before progression and the start of new anti-cancer therapy but not qualifying as CR or PR.

PD: Progression documented after start date and not qualifying as CR, PR or SD.

Not Evaluable (NE): All other cases. Note that reasons for NE should be summarized and the following reasons could be used:

- Early death : death prior to 6 weeks after start date
- No post-baseline assessments
- All post-baseline assessments have overall response NE
- New anti-cancer therapy started before first post-baseline assessment
- SD too early (< 6 (-5 days) weeks after start date)

Special and rare cases where BOR is NE due to early SD will be classified as ‘SD too early’.

irRECIST

In addition to the RECIST 1.1, this study is also assessing patients' response using irRECIST criteria.

For irRECIST, with the exception of a complete response assessment, only target and new measurable lesions are taken into account. In contrast to RECIST v1.1, the irRECIST:

Requires confirmation of both progression and response by imaging at least 4 weeks from the date first documented, and

Does not necessarily score the appearance of new lesions as progressive disease if the sum of lesion diameters of target lesions (maximum of 5 target lesions, maximum of 2 per organ) and measurable new lesions does not increase by $\geq 20\%$.

The same method of assessment and the same technique should be used to characterize each identified and reported target lesion(s) at baseline and throughout the study.

irRECIST responses are defined as follows:

- **Overall immune-related complete response (irCR):** Complete disappearance of all lesions (whether measurable or not) and no new lesions. All measurable lymph nodes also must have a reduction in short axis to <10 mm.
- **Overall immune-related partial response (irPR):** Sum of the diameters (longest for non-nodal lesions, shortest for nodal lesions) of target and new measurable lesions decreases $\geq 30\%$.
- **Overall immune-related stable disease (irSD):** Sum of the diameters (longest for non-nodal lesions, shortest for nodal lesions) of target and new measurable lesions does not meet criteria for irCR or irPR, (compared to baseline) or immune-related progressive disease (irPD, compared to nadir).

- **Overall immune-related progressive disease (irPD):** Sum of the diameters (longest for non-nodal lesions, shortest for nodal lesions) of target and new measurable lesions increases $\geq 20\%$ (compared to nadir) with a minimum absolute increase of 5 mm, confirmed by a repeat, consecutive observation at least 4 weeks from the date first documented.

New measurable lesions: Incorporated into tumor burden (ie, added to the target lesion measurements). In order to be selected as new measurable lesions (≤ 2 lesions per organ, ≤ 5 lesions total, per timepoint), new lesions must meet criteria as defined for baseline target lesion selection and meet the same minimum size requirements of 10 mm in long diameter and minimum 15 mm in short axis for new measurable lymph nodes. New measurable lesions shall be prioritized according to size, and the largest lesions shall be selected as new measured lesions.

New non-measurable lesions: Do not define progression but preclude irCR.

Table 2. Overall Responses Derived from Changes in Target, Non-target, and New Lesions

Measurable disease	Non-measurable disease		
Target and New Measurable Lesions (Tumor Burden) ^a	Non-Target Lesions	New, non-measurable Lesions	Overall response using irRECIST ^b
Decrease 100%	Absent	Absent	irCR
Decrease 100%	Stable	Any	irPR
Decrease 100%	Unequivocal progression	Any	irPR
Decrease $\geq 30\%$	Absent/stable	Any	irPR
Decrease $\geq 30\%$	Unequivocal progression	Any	irPR
Decrease $< 30\%$ and increase $< 20\%$	Absent/stable	Any	irSD
Decrease $< 30\%$ and increase $< 20\%$	Unequivocal progression	Any	irSD
Increase $\geq 20\%$	Any	Any	irPD

^a Decreases assessed relative to baseline

^b Response (irCR and irPR) and progression (irPD) must be confirmed by a second, consecutive assessment at least 4 weeks apart.

Derivation of BOR and irBOR

Examples of objective status sequences and overall response for a tumor assessment interval of at least 4 weeks and at least as long as the minimum assessment time to qualify as SD are shown in [Table 3](#). This will vary for other assessment schedules.

The best overall response is the best response recorded from the start of the study treatment until the end of treatment without requirement for confirmation. The patient's best overall response assignment will depend on the findings of both target and non-target disease and will also take into consideration the appearance of new lesions.

Table 3. Scenarios of Assignments of Best Overall Response (irBOR) using irRECIST where Confirmation of Response or Progression is Required

Objective status at:				
Assessment 1	Assessment 2	Assessment 3	Assessment 4	ir Best Overall Response
Death				NE
irCR	irCR	irPD		irCR
irCR	NE	irCR	irPD	irCR
irPR	irCR	irCR	irPD	irCR
irPR	irCR	irPD		irPR
irPR	irPR	irPD		irPR
irPR	irSD or NE	irPR	irPD	irPR ^a
irPR	irPD	irPR		irSD
irPR	irPR	irCR	irPD	irPR
irCR	irPR			irPR
irCR	irPD			irSD
irPR	irPD			irSD
irSD or NE	irCR	irPD		irSD
irSD or NE	irPR	irPD		irSD
irSD	irPD			irSD
irPD	irPD			irPD
irPD	Death			irPD ^b
irPD				NE
No or NE assessment				NE
NE	irPD			NE
NE	No or NE assessment			NE
NE	NE	irPD		NE

a. if irPRs are at least 4 weeks apart. b. Death due to disease progression.

- Duration of Stable Disease - Duration of stable disease is defined from the start of the treatment until the criteria for progression are met, taking as reference the smallest tumor measurements recorded since the treatment started, including the baseline measurements. This endpoint is applicable to the subset of patients who achieved a best overall response of stable disease (SD), those patients whose best overall response is not SD will be excluded from this endpoint analysis. A minimum of 6 weeks (with a - 5 days window, which is essentially a minimum of 37 days) interval of two assessments is required for this endpoint.

- Progression free survival (PFS) – PFS is the time from randomization date to date of first documentation of PD based on RECIST, irRECIST or death due to any cause.

Table 4. PFS Outcome and Event Dates

Situation	Date of Progression/Censoring	Outcome
No adequate baseline assessment	Start date	Censored
PD or death \leq 12 weeks after last adequate tumor assessment	Date of PD or death	Event
No PD but withdraw due to clinical progression	Date of last adequate tumor assessment	Event
PD or death $>$ 12 weeks after the last adequate tumor assessment ^a	Date of last adequate tumor assessment ^a documenting no PD prior to new anti-cancer therapy or missed assessments	Censored
No PD		
New anti-cancer therapy given		

^a If there are no adequate post-baseline assessments prior to the PD or death, then the time without adequate assessment should be measured from the start date; if the criteria were met the censoring will be on the start date.

Reasons for censoring should be summarized according to the categories in Table 5.

Table 5. PFS Censoring Reasons and Hierarchy

Hierarchy	Condition	Censoring Reason
1	No adequate baseline assessment	No adequate baseline assessment
2	Start of new anti-cancer therapy before event.	Start of new anti-cancer therapy
3	Event more than 12 weeks from last adequate post-baseline tumor assessment/start date	Event after missing assessments ^a
4	No event and [withdrawal of consent date \geq start date OR End of study (EOS) = Subject refused further FU]	Withdrawal of consent
5	No event and lost to follow-up in any disposition page	Lost to follow-up
6	No event and [EOS present OR disposition page for any EPOCH after screening says patient will not continue into any subsequent phase of the study] and no adequate post-baseline tumor assessment	No adequate post-baseline tumor assessment
7	No event and none of the conditions in the prior hierarchy are met	Ongoing without an event

^a more than 12 weeks after last adequate tumor assessment.

- Disease Control (DC) – a patient with a BOR of CR, PR, or SD is defined as having DC. The DC rate is defined as the percentage of patients with DC according to the appropriate analysis set. In addition, a DC rate at week X would be to calculate a PFS Kaplan Meier rate at week X.
- Duration of Response (DoR) – for patients with an objective response, DoR is the time from first documentation of PR or CR to date of first documentation of PD or death due to any cause.

Censoring: Same as censoring for primary definition of progression free survival (PFS) used in the study. Duration of response is only calculated on the subset of patients having CR or PR.

- Time to progression (TTP) - TTP is the time from start date to the date of the first documentation of PD.

In TTP analysis, deaths are censored, either at the time of death or at an earlier visit representing informative censoring (non-random pattern of loss from the study).

Censoring: Same as censoring for the definition of PFS. In addition patients who die without PD will be censored on the date of the last adequate tumor assessment that documented no progression.

Events and censoring rules are summarized in Table 6 similarly to PFS but not including death as an event.

Table 6. TTP Outcome and Event Dates

Situation	Date of Progression/Censoring	Outcome
No adequate baseline assessment	Start date	Censored
PD \leq 12 weeks after last adequate tumor assessment or \leq 12 weeks after start date	Date of PD	Event
No PD/ withdraw due to clinical progression	Date of last adequate tumor assessment	Event
PD $>$ 12 weeks after the last adequate tumor assessment ^a	Date of last adequate tumor assessment ^a documenting no PD prior to new anti-cancer therapy or missed visits.	Censored
No PD		
New anti-cancer therapy given		
Death due to any cause		

^a If there are no adequate post-baseline assessments prior to the PD or death, then the time without adequate assessment should be measured from the start date; if the criteria were met the censoring will be on the start date.

Reasons for censoring should be summarized according to the categories in [Table 7](#).

Table 7. TTP Censoring Reasons and Hierarchy

Hierarchy	Condition	Censoring Reason
1	No adequate baseline assessment	No adequate baseline assessment
2	Start of new anti-cancer therapy before PD.	Start of new anti-cancer therapy
3	Event more than 12 weeks from last adequate post-baseline tumor assessment/start date	Event after missing assessments ^a
4	Death prior to PD	Death due to any cause
4	No PD and [withdrawal of consent date \geq start date OR End of study (EOS) = Subject refused further FU]	Withdrawal of consent
5	No PD and lost to follow-up in any disposition page	Lost to follow-up
6	No PD and EOS present OR disposition page after screening says patient will not continue into any subsequent phase of the study, and no adequate post-baseline tumor assessment	No post-baseline tumor assessment
7	No PD and none of the conditions in the prior hierarchy are met	Ongoing without an event

^a more than *12 weeks* after last adequate tumor assessment.

DC, DoR, DoSD, PFS and TTP will be assessed based on RECIST and irRECIST criteria, respectively.

- Overall Survival (OS);
- Overall Survival Rate at 6 months, 1 year and 2 years.

Overall survival is the time from start date to date of death due to any cause.

Censoring: Patients last known to be alive are censored at date of last contact.

Date of Last Contact

The date of last contact will be derived for patients not known to have died at the analysis data cutoff date using the latest complete date (non-imputed) among the following:

- All patient assessment dates (eg, blood draws [laboratory, PK], vital signs, performance status, ECG, tumor assessments, concomitant radiation, surgery);
- Start and end dates of follow-up anti-cancer therapies;
- AE start and end dates;

- Last date of contact where “Subject Remains in Follow-up” collected on the “Survival Follow-up” eCRF (do not use date of survival follow-up assessment unless status is alive);
- Study drug start and end dates;
- Randomization date;
- Date of discontinuation on disposition eCRF pages (do not use if reason for discontinuation is lost to follow-up or death).

Note:

- Only dates associated with patient visits or actual examinations of the patient should be used. Dates associated with a technical operation unrelated to patient status (eg, the date a blood sample was processed) should not be used.
- Assessment dates after the cutoff date will not be applied to derive the last contact date.

Follow-up time for Overall Survival

A variety of methods are used to summarize the extent of follow-up in a study with censoring, as described by Schemper et al (1996), including:

- Reversing the censoring and event indicators and estimating follow-up time with the method of Kaplan and Meier (referred to as the “Kaplan-Meier potential follow-up or reversed Kaplan-Meier method”).
- Calculating the “observation time” (start date to date of death or last contact date) and presenting descriptively.
- Calculating “censoring time” (start date to date of last contact for those without event) to evaluate if one treatment arm has much larger values than the other.
- Other methods as presented in Schemper et al (1996).

Preliminary evidence of anti-tumor activity based on response rate (RR), as assessed using the RECIST version 1.1, and /or irRECIST

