- Overall immune-related partial response (irPR): Sum of the longest diameters of target and new measurable lesions decreases ≥30%.

- Overall immune-related stable disease (irSD): Sum of the longest diameters of target and new measurable lesions neither irCR, irPR, (compared to baseline) or immune-related progressive disease (irPD, compared to nadir).
- Overall immune-related progressive disease (irPD): Sum of the longest diameters of target and new measurable lesions increases ≥20% (compared to nadir) with a minimum absolute increase of 5 mm, confirmed by a repeat, consecutive observation at least 4 weeks from the date first documented.

New measurable lesions: Incorporated into tumor burden.

In order to be selected as new measurable lesions ( $\leq 2$  lesions per organ,  $\leq 5$  lesions total, per timepoint), new lesions must meet criteria as defined for baseline target lesion selection and meet the same minimum size requirements of 10 mm in long diameter and minimum 15 mm in short axis for new measurable lymph nodes. New measurable lesions shall be prioritized according to size, and the largest lesions shall be selected as new measured lesions.

All new lesions not selected as new measurable lesions are considered new non-measurable lesions and are followed qualitatively.

New non-measurable lesions: Do not define progression but preclude irCR.

Table 10. Overall Responses derived from Changes in Index, Non-index, and New Lesions

Measurable	Non-Measurable Response		Overall Response
Response Tumor burden a	Non-index lesions	New, non-measurable lesions	using irRECIST b
↓ 100%	Absent	Absent	irCR
↓ 100%	Stable	Any	irPR
↓ 100%	Unequivocal Progression	Any	irPR
↓≥30%	Absent/ stable	Any	irPR
↓≥30%	Unequivocal Progression	Any	irPR
↓ <30% and ↑<20%	Absent/ Stable	Any	irSD
↓ <30% and ↑<20%	Unequivocal Progression	Any	irSD
↑≥20%	Any	Any	irPD

<sup>a Decreases assessed relative to baseline.

<sup>b Response (irCR and irPR) and progression (irPD) must be confirmed by a second, consecutive assessment at least 4 weeks part.

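### SAP Tables 2 and 3 give different irRECIST best responses when an irSD scan falls between two irPR scans

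*SAP*

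**What the plan says.** All the SAP text is in Section 5.8, Efficacy Endpoints.

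- **SAP Table 2, footnote b:** "Response (irCR and irPR) and progression (irPD) must be confirmed by a second, consecutive assessment at least 4 weeks apart".
- **Protocol Appendix 6, Table 10, footnote b:** the same rule; response and progression "must be confirmed by a second, consecutive assessment at least 4 weeks part".
- **SAP Table 3** is titled "Scenarios of Assignments of Best Overall Response (irBOR) using irRECIST where Confirmation of Response or Progression is Required". One row starts with irPR at assessment 1 and continues "irSD or NE irPR irPD irPR ^a": the second assessment is irSD or NE, the third irPR, the fourth irPD, and the assigned best response is irPR. Its only condition is footnote a, "if irPRs are at least 4 weeks apart". A second row scores irCR, NE, irCR, irPD as irCR.
- **SAP irRECIST text before Table 2:** irRECIST "Requires confirmation of both progression and response by imaging at least 4 weeks from the date first documented". It does not say that the confirming scan must be consecutive.
- **SAP text just before Table 3**, under the subheading that covers both BOR and irBOR: "The best overall response is the best response recorded from the start of the study treatment until the end of treatment without requirement for confirmation". That sentence is not limited to RECIST 1.1.

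**The concern.** Footnote b makes the next assessment the one that confirms a response. In the Table 3 row, the next assessment is an irSD scan. It was read, and it did not confirm. Two rules in one SAP section therefore classify the same scans differently, one as a response and the other not.

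Objective response by irRECIST is a secondary endpoint in all four parts, and Section 5.8 defines ORR as the percentage with a best response of CR or PR. The reported irRECIST ORR would then depend on which table is programmed. Membership of the duration-of-response and duration-of-stable-disease subsets would depend on it too. The trial is open label, so the rule should be settled before anyone knows which patients it affects.

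**Working it through.** **Inputs.** The sequences and assigned best responses come from SAP Table 3, and the confirmation rule from SAP Table 2 footnote b. Scan intervals come from the protocol Schedules of Activities: every 6 weeks in A1 and B1, and every 8 weeks for the first 24 weeks in A2 and B2. The arm size of about 20 is that of A2, and up to 20 for B2. Confidence limits for scale use the method of protocol Table 7.

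**Step 1: does footnote a screen the row out?** On the scheduled grid, assessments 1 and 3 are 2 × 6 = 12 weeks apart in A1/B1 and 2 × 8 = 16 weeks apart in A2/B2. Both exceed 4 weeks, so the condition is met and the row applies.

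**Step 2: can the sequence arise under the definitions?** Take hypothetical tumour sums of 68%, 73% and 67% of baseline. The decreases are 32%, 27% and 33%. The rise from the nadir at the second scan is (73 − 68)/68 = 7%, below the 20% for irPD. The statuses are irPR, irSD, irPR. This shows that the pattern is possible, not how common it is.

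**Step 3: which reading of confirmation reproduces Table 3?** Table 3 has 22 rows. Splitting the three that allow either irSD or NE gives 25 sequences. An irPR may be confirmed by irPR or irCR. An unconfirmed response falls to irSD, as in Table 3's own rows irPR, irPD = irSD and irPR, irPD, irPR = irSD.

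| Reading of the confirming assessment | Disagreements with Table 3 (of 25) | Sequences |
|---|---|---|
| Strictly the next assessment | 3 | irPR-irSD-irPR-irPD; irPR-NE-irPR-irPD; irCR-NE-irCR-irPD |
| Next evaluable assessment (NE skipped) | 1 | irPR-irSD-irPR-irPD |
| A later assessment; irSD or NE may intervene, irPD may not | 0 | none |

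The generous reading of consecutive removes both NE disagreements. It does not remove the irSD one, because an irSD scan is evaluable.

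**Step 4: size.** One reclassified patient changes ORR by 1/20 = 5 percentage points. Protocol Table 7 is reproduced by p ± 1.645 × √(p(1 − p)/20) + 1/40 (the 1/40 widens each side, and the lower limit is cut at 0):

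- 2/20: 1.645 × √(0.10 × 0.90/20) = 0.110; upper limit 0.10 + 0.110 + 0.025 = 23.5%, as printed.
- 1/20: 1.645 × √(0.05 × 0.95/20) = 0.080; upper limit 0.05 + 0.080 + 0.025 = 15.5%, as printed.

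For example, moving one of two responders to irSD takes the result from 10% (90% CI 0 to 23.5%) to 5% (0 to 15.5%).

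**Step 5: which endpoints move?** Duration of response covers only patients with CR or PR, and duration of stable disease only those whose best response is SD, so the patient changes subset. Disease control counts CR, PR and SD, so it does not change. RECIST 1.1 response needs no confirmation under Section 5.8, so it does not change either.

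**The case against.** The best defence is that Table 3 is the specific irBOR derivation and should govern. It carries its own condition for the disputed row, is internally coherent, and agrees with the SAP's general irRECIST sentence. Among the SAP's response definitions, only irPD asks for a consecutive repeat observation. On this view the outlier is one word in one footnote, and the SAP introduction says that the SAP supersedes the protocol's statistical considerations. Much of this stands, and it is why the fix follows Table 3. It does not remove the contradiction: both tables are in the SAP, neither is given precedence, and Appendix 1.3, where endpoints were to be defined further, is still to be determined. The remark that the examples vary with other schedules concerns scan spacing.

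A reader might infer more than the documents support:

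- *That the NE rows are in plain conflict.* They conflict only if consecutive is read strictly. Read as the next evaluable scan, they agree with footnote b.
- *That disease control changes.* It does not, because irPR and irSD both count.
- *That the B2 continuation rule could flip.* The rule (protocol 3.1.2.2, SAP Section 3) names neither irRECIST nor confirmation, and says only that enrollment may stop. At the 16-week assessment the tenth patient has had 16/8 = 2 scheduled post-baseline scans, and the pattern needs three. It could matter only for an earlier enrollee who is the sole responder, under a confirmed-irRECIST reading that the documents do not state.
- *That the pattern is frequent.* Nothing in the documents gives a rate.

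**Conclusion.** The contradiction is real and confined to one sequence on any reading: irPR, irSD, irPR, irPD, with no consecutive pair of responses. Table 3 makes the patient an irRECIST responder; footnote b does not. Scoring that patient irSD under footnote b is an inference from Table 3's other unconfirmed-response rows, since footnote b names no category.

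The effect is 5 percentage points of irRECIST ORR per affected patient in a 20-patient arm, plus a change of duration subset. The endpoint is secondary, the summaries are non-inferential (SAP 7.1), and the number of affected patients cannot be known from the documents. No effect on the B2 continuation rule is shown. The sentence that drops confirmation for best overall response adds a possible third rule if it is applied to irBOR. The point merits correction before database lock because the two rules cannot both be programmed and the repair is small.

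**What to change.** Make these edits before database lock:

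1. In SAP Table 2 footnote b, for irCR and irPR, replace the requirement for a second, consecutive assessment with: *a subsequent assessment at least 4 weeks after first documentation, with intervening irSD or NE allowed but no intervening irPD*. Keep consecutive for irPD. This agrees with the SAP's general irRECIST sentence and reproduces every Table 3 row, so Table 3 needs no edit.
2. Limit the no-confirmation sentence before Table 3 to RECIST 1.1.
3. Record in the SAP that the response rule departs from protocol Table 10 footnote b. The SAP introduction already undertakes to identify substantial differences from the protocol.
4. Carry the rule into the derivation specification, including that irPR may be confirmed by irPR or irCR, as Table 3 implies.

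The cost is one footnote, one qualified sentence, one note of departure and the matching program logic. No data collection changes. Changing the Table 3 rows to irSD instead would be a poorer choice: applied to whole rows, it would also downgrade the NE sequences, where a conflict exists only on the strict reading.
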